The sample size was generated using G*Power (Version 3.1.9.6). Using the peak power variable in a study analysing ASH and muscle soreness (Diehl, 2021), the estimate of the effect size of Cohen's d equals to 0.53 and therefore used in the sample size calculation for this proposed research. There is no further calculation to convert Cohen's d into Cohen's f to make it appropriate for ANOVA, as when there are only two groups Cohen's f is the same as Cohen's d (University of Michigan, 2021). Using ANOVA repeated measures between factors, effect size of 0.53, 80% power, 5% risk error in a two-parallel-group design and three measurements, the overall sample size is 30 participants, with 15 subjects per group. The calculation provided by G*Power can be found in the appendix.

Selection criteria

Inclusion for participants who are:

- Female
- Playing football professionally
- At a sub-elite to elite standard

- Healthy and free of disease

Exclusion for participants with:

- Active supplementation with other ergogenic aids
- Medication or contraceptives (to not interfere with existing treatment)
- Thyroid conditions (due to interaction with cortisol)
- Diabetes or certain autoimmune conditions (to not interfere with existing treatment)
- Active pregnancy (to not interfere with existing treatment)
- Allergies to nightshades such as tomato, aubergine, potatoes and peppers (as ASH is an herb in the nightshade group)
- No signing of the consent form

The withdrawal criteria will be participants who request to withdraw and do not wish to proceed, or do not complete the required study tests.

Intervention

The intervention will be 600mg of KSM-66, a branded supplement derived from the root extract of the herb ashwagandha, with a consistent rate of 5% withanolides for 28 days. It is the most clinically studied extract of the herb and is the only type of ashwagandha to receive third party testing certification (Informed Sport, Informed Ingredient, BSCG, Clean Label Project). The laboratory where the product is made, Ixoreal Biomed, has received Current Good Laboratory Practices (cGLP), quality controlled and tested against heavy metals and pesticides.

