Food diary analysis research, compared against (Dobrowolski et al., 2020):

- Energy intake (kcal)
- Energy availability (kcal/kg fat free mass/day)
- Protein (g/day)
- Carbohydrates (g/day)
- Fat (%)
- Fluids (L/day)
- Vitamin D (mg/day)
- Calcium (mg/day)
- Iron (mg/day)

All data will be collected via Snap-N-Send and stored using Nutritics dietary analysis software (Research Edition, v5.096, Dublin, Nutritics, 2019). The Snap-N-Send method was analysed in a doubly labelled water study and was shown to have enhanced validity for assessing athlete total energy intake (Costello et al., 2019). The Nutritics software was clinically studied to be a useful and valid tool for healthcare professionals to measure macronutrients and micronutrients, demonstrating that its analysis values positively correlated with plasma markers (Watkins et al., 2020)

Independent:

- The treatment of ASH: 600mg KSM66 (30mg withanolides) once a day for 28 days

Data collection

Study data will be collected manually and entered into Blanquerna's OneDrive system. All data sheets and files will be backed up on to Google Sheets and shared with associated researchers and tutors of the project. This allows for data to be reviewed by collaborators.

Dietary intake data will be collected via Whatsapp using Snap-N-Send. The data will then be manually entered and stored using Nutritics and access will be shared with collaborators.

Data analysis

For the muscle strength and recovery research, dependent variables will be described as the mean and standard deviation and calculated using and **ANOVA repeated measures, between factors** as there will be three time points. A descriptive analysis will be carried out for all the data collected in the data collection notebook. To assess the normality of the data distribution, the **Kolmogorov-Smirnov** test will be used.

For the food diary analysis, dependent variables will be described as the mean and standard deviation and determined using **one-sided t-test** to compare against data averages of nutritional recommendations for female footballers (Dobrowolski et al., 2020). **Pearson's r** will be used to examine correlations between the selected variables.

Ethical considerations

The ethical considerations for this study are predominantly the safety, comfort and consent of the participant:

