- Epistemic injustice will be avoided in the study by the researcher listening to the participant and valuing their opinion and feelings on the research subject
- The safety and tolerability of ASH has been clinically studied in humans and mice and is deemed safe to ingest. However, participants will be informed of rare, potential side effects and their right to leave the study at any time
- Personal information (name, contact details) of the participant will not be shared with a wider network or in the research papers, but will be used by the researcher during the study to check-in on the participant. They will be contacted for their questionnaire scores during the research on perceptive muscle recovery – if the participant does not agree to this method, they may decline or drop out of the study
- There will be data collection during the study, and it is important to not violate the participants right to privacy when asking personal questions via the questionnaires. The participant may decline to answer any question they deem unsuitable
- Participants will be made aware that they will be observed for the data collection during the study and may decline this if it makes them uncomfortable
- If the researcher fails to respect personal, cultural or religious values that makes the participant feel uncomfortable, they have the right to drop out of the study
- The participants will be informed about the aims of the study and will be asked to sign an informed consent form (the form can be found in the appendix)

Scientific and social value

The study is contributing to the generation of scientific knowledge. For a supplement that is widely used, the existing knowledge on its effects on athletes and females is substantially low. In addition, there is very little existing research on short-term supplementation of ASH as the focus is currently on 8-12 weeks supplementation. This study will inform as to whether the supplement can provide performance benefits after 28 days, as the author believes this is a more realistic and safer dosage duration. This research therefore holds relevance in scientific advancements and may provide new dosage guidelines to users. Another aspect of scientific

relevance is the response to the public calls for more research on this specific area of ASH and sports performance.

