There is high social relevance and value for the female athlete population, who are likely to experience strict training schedules with limited recovery time between training and matches. If significant benefits are found in recovery from ASH, there is a safe and low-cost method for athletes to adapt into their routine. Additionally, if there are benefits found in this thesis, practitioners who work directly with female athletes will be informed of up-to-date practice with ASH and can pass on information to athletes. Importantly, if the thesis shows no benefits across any measures, both athletes and practitioners will be informed of the supplement and its credibility.

The study holds high social and innovative relevance as it will collect, summarise and present existing published research that indicates a) overuse in high dosage and duration may lead to consistently lowered cortisol and b) consumption of solely root extraction of the herb is highly recommended in order to avoid potentially ingesting the cytotoxic metabolites of Withaferin A and Withanone, which are found in the leaves of the herb. Providing safety and information for users and future users of ASH is the crux of this thesis.

Scientific-technical validity

All of the instruments and questionnaires used in the proposed study are established in peer-reviewed literature and deemed both valid and reliable. Two measures will be taken for each tool. The first instance will be the baseline measure and will occur on-site at the training ground gym in the evening during a typical training session. The second measure will take place after 28 days of supplementation (half ASH, half placebo) in the same location and time of day. Each participant will be given a timeslot to enter the gym and perform their assessments before continuing with normal resistance-training session. The tests using instruments will be monitored by two strength and conditioning coaches, and the data will be collected by two sports scientists. The following evaluation instruments are as follows:

- Hand grip strength of the participants will be measured with a CAMRY dynamometer and the predominant measure to assess muscle strength. It is a commonly used tool in sports performance and demonstrates validity and reliability in relation to athlete

strength (Cronin et al., 2017). The validity for the use of a CAMRY dynamometer is documented by (Huang et al., 2022) when comparing against the Jamar dynamometer.

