There is a high likelihood that the study may impact the target population of female footballers and to athletes as a wider population. The supplement of KSM-66 is easily accessible, cost-effective and has Informed Sport certification, making it safe to ingest without the risk of contaminated ingredients. The supplement is already highly used in the area of sports performance; importantly, this study aims to verify whether short-term supplementation has benefits and will inform the wider population on safe dosage guidelines. This benefits not only athletes, but practitioners on best procedure for their patients or clients. Weekly gym sessions are an integral part of footballer's training regime, and if benefits are found in muscle strength, RPE and wellness scores of sleep quality, muscle soreness, stress and fatigue, athletes may wish to explore supplementation with KSM-66 to improve their strength output, perception of difficulty, sleep quality and muscle soreness with a safe method. Additionally, if athletes or active individuals experience high levels of stress and it affects their performance and recovery as a result, the study is applicable as the intervention may potentially improve these areas.

Limitations

Regarding participants, accuracy of food reporting and following supplementation guidelines will be based on trust between the author and participant. The study has convenience sampling, which allows for ease of data collection but lacks generalisability in the sample. The focus of the study is on subjective results, without the validity of physiological tests that could measure metabolic markers, such as cortisol, from blood samples. There is also a lack of

previous research on ASH and exercise in females and athletes, which impacts result credibility.

Dissemination plan

Full transparency of the measurements will be published within each of the corresponding three papers. No measurements or scores will be omitted. The purpose of the outreach is to contribute to the scientific knowledge of ASH and its effects on muscle strength and recovery in female athletes. Additionally, this research will provide scientific knowledge to sports science and the industry of sports nutrition of the influence of short-term ASH, and whether it provides any benefits to female athletes. The methods of sharing the scientific knowledge will include presentations at conferences, exhibitions, social media and published articles in journals.

References

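### The plan counts a player who misses required tests as withdrawn and names only a three-time-point ANOVA; no analysis set or missing-data method says how incomplete players enter the group comparison

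*Combined protocol and SAP*

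**What the plan says.** All places are in the combined protocol and SAP.

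- **Selection criteria** gives two routes to withdrawal, a request and non-completion: "The withdrawal criteria will be participants who request to withdraw and do not wish to proceed, or do not complete the required study tests".
- **Sample size** rests on a repeated-measures ANOVA "in a two-parallel-group design and three measurements, the overall sample size is 30 participants, with 15 subjects per group". The text states no allowance for loss. The appendix calculation it points to is not readable in the copy reviewed.
- **Data analysis** names "ANOVA repeated measures, between factors" for the trial outcomes, "as there will be three time points". The Kolmogorov-Smirnov test is a normality check. The one-sided t-test and Pearson correlation belong to the food diary study.
- Two statements come close to a rule on inclusion. Data analysis says: "A descriptive analysis will be carried out for all the data collected in the data collection notebook". The Dissemination plan says: "No measurements or scores will be omitted".
- **Ethical considerations** allows gaps within a questionnaire: "The participant may decline to answer any question they deem unsuitable".
- **Scientific-technical validity** says "Two measures will be taken for each tool" and describes baseline and day 28. The Work plan schedules strength tests at baseline, day 14 and day 28, each followed by recovery scores the next day.

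The supplied text contains no analysis set, no missing-data method and no provision for collecting data after withdrawal.

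**The concern.** Two separate events appear to be merged: missing an assessment and leaving the trial. A player absent from one gym session meets the withdrawal criterion as worded, and a standard repeated-measures ANOVA would drop her record in any case. A day-28 value that was actually measured could then play no part in the comparison.

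Twelve training sessions and four matches fall within the 28 days, so misses through soreness, fatigue or injury are plausible, and these lie close to what the trial measures. If misses relate to those states, the players compared are no longer the groups as randomised, and the direction of any bias is unknown. With 15 per arm, each exclusion removes 1/15, or about 7%, of an arm.

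**Working it through.** **1. Do the near-rules settle who is compared?** The promise to describe all collected data concerns description. The promise to omit no scores stands in a section on publication. Neither says how a player with two of three values enters the ANOVA. If every score is meant to count, the usual ANOVA does not deliver that.

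**2. Is it clear what counts as incomplete?** A player who misses only day 14 has both measures described under Scientific-technical validity, but only two of the three stated or scheduled under Sample size, Data analysis and Work plan. The withdrawal criterion cannot be applied consistently until these are reconciled. It is also unstated whether a declined question makes a test incomplete.

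**3. The plan's own figure.** For the between-factors test, λ = f²·N·m/(1+(m−1)ρ), with 1 and N−2 degrees of freedom and alpha 0.05. With f = 0.53 as entered, N = 30 is reproduced for m = 3 if ρ is 0.9 to 1.0 (power 0.83 to 0.80), or for m = 1 (power 0.8001). I use only the arm size of 15. The plan enters Cohen's d as Cohen's f, which is a separate error, so I draw no power figure here.

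**4. Loss.** The documents give no miss rates. Assume independent misses with probability q = 0.02 or 0.05 per occasion; clustering in the same players would lower these figures.

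- Lacking at least one of three values for an outcome: 1−(1−q)³ = 0.059 or 0.143. Times 30, this is 1.8 or 4.3 players.
- Share of those who still have day 28: [(1−q)−(1−q)³]/[1−(1−q)³] = 0.66 or 0.65.

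**5. Bias, extreme illustration.** Assume no true effect, 15 per arm, equal correlation ρ of 0.5 to 0.9 between visits, and SD of a single visit = 1. In one arm only, the one or two players with the lowest day-14 values miss day 28 and are dropped. The expected two lowest of 15 standard normals are −1.736 and −1.248. The arm's day-14 mean therefore shifts by 1.736/14 = 0.124 SD (one player) or 2.984/13 = 0.230 SD (two). Each contrast takes a multiple of this:

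| Complete-case contrast | Multiplier | One dropped | Two dropped |
|---|---|---|---|
| Three-visit mean (between-groups effect) | (1+2ρ)/3 | 0.08–0.12 | 0.15–0.21 |
| Raw day-28 difference | ρ | 0.06–0.11 | 0.11–0.21 |
| Baseline-to-day-14 change | 1−ρ | 0.01–0.06 | 0.02–0.11 |
| Baseline-to-day-28 change | ρ−ρ = 0 | 0 | 0 |

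Simulation (20,000 trials per setting) agrees with the first and last rows to within 0.01 SD. For scale, the standard error of the three-visit difference with full arms is √[(2/15)(1+2ρ)/3] = 0.30 to 0.35. The first-row shifts are therefore about 0.3 to 0.6 of a standard error.

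**6. What a mixed model recovers.** In the scenario of step 5, a baseline-adjusted likelihood estimate that uses the day-14 values has at most about 0.003 SD bias. That follows from the set-up, because missingness was made to depend on an observed value. If instead the players with the lowest day-28 values miss day 28, the bias left is roughly (1−R²) times 0.124 or 0.230, where R² = 2ρ²/(1+ρ) runs from 0.33 to 0.85. This gives about 0.02–0.08 SD (one) or 0.03–0.15 SD (two), and simulation agrees to within 0.01 SD. The raw complete-case day-28 difference is biased by 0.12 or 0.23 SD in that case.

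**The case against.** The strongest reply has four parts.

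- **The plan never says completers only.** A reader might infer that it prescribes such an analysis. It does not: that reading joins the withdrawal criterion to the default behaviour of the ANOVA. What stands is that nothing in the plan points the other way.
- **The bias may be nil.** A reader might infer a bias of up to about 0.2 SD in the planned analysis. The documents do not support that as an expected size. The scenario takes the very lowest players from one arm and none from the other, and a baseline-to-day-28 change is unaffected under equal correlations. It also concerns players who miss day 28, not those in step 4 who keep it; for the latter no bias figure is available. However, the effect named under Sample size and Data analysis is the between-factors one, which does shift.
- **Misses are made unlikely.** Individual timeslots in regular sessions, remote collection of recovery scores, reminders and a one-week check-in all help, and the miss rates used above are assumed. This lowers the expected loss but supplies no rule for the misses that occur.
- **Required tests may mean only the instrument tests, and one sentence could close the gap.** The first is possible: the link from declined questions to withdrawal is weak. The second is partly right, since a short definition would remove the ambiguity. A sentence confirming complete cases would still discard measured day-28 values.

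**Conclusion.** The concern holds as a gap that should be closed before unblinding. Non-completion is a withdrawal criterion, the only named group comparison ordinarily uses complete records, and no analysis set or missing-data method says who is compared. That conclusion needs none of the numbers.

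On size, a handful of players is at stake, and roughly two thirds of those with an incomplete record would still have a day-28 value, given the assumed 2% or 5% independent miss rates. Bias ranges from about zero to about 0.21 SD in a deliberately extreme case, depending on the effect read, on one or two players being lost and on correlations of 0.5 to 0.9. Nor should a reader infer that a mixed model removes bias altogether: it does so when misses depend on observed values, and only in part when they depend on the unobserved day-28 state. Confidence is medium, because the harm depends on misses that the documents do not quantify.

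**What to change.** 1. State that a missed test or declined question does not by itself remove a player from the analysis, and that later assessments continue where she agrees.
2. Replace the ANOVA with an analysis of all randomised players in their allocated group: a mixed model on the two post-baseline values, with baseline as covariate, group by visit, unstructured covariance and a small-sample degrees-of-freedom correction such as Satterthwaite or Kenward-Roger. Other likelihood-based choices would also serve; the essential points are the analysis set and the use of partial records.
3. State a rule for a missing baseline, such as mean imputation or a constrained longitudinal model. Otherwise that player leaves the model for that outcome.
4. Report completers as a sensitivity analysis, and missing values with reasons by arm.
5. Reconcile the two measures under Scientific-technical validity with the three under Sample size, Data analysis and Work plan, so that the required tests are defined.

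**Cost.** Wording, and the mixed-model procedure in the SPSS already planned; no extra players or visits. The downside is the missing-at-random assumption, which can fail, for example when an unrecorded injury causes the miss. Power should be restated only once the separate effect-size error is corrected. Rules for stopping the supplement or for safety withdrawal are left to the sponsor.

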There is no known conflict of interest in this study. There will be no plagiarism within this study and all words will be original to the study. There will be no fabrication or invention of results, and data will be analysed and published accurately and transparently. All collaborators will be employed staff members of the football club who are collaborating in the thesis. The gym facilities where the tests will be measured and performed are on-site of the football club and where the players have weekly gym training sessions. The gym facility is a licensed establishment. The participants will be informed of the results and will have access to their individual data.

Work plan

A visual representation of the study timeline can be found in the appendix. A description of each step is as follows:

0. Approval from the ethical committee
1. Participants are informed about the aims of the study and sign the consent form. Information about age, BMI, years of practice and health history is collected
2. Participants start tracking their food diaries via an app remotely for three days over the weekend prior to the supplementation for familiarisation
3. Baseline measures for muscle strength will be taken on the following day at the club gym, coinciding with a regular gym training session. The measures will be taken prior to starting a typical training session
4. The team will consist of the author ([name]), [name] and [name] who will assist with data collection and physiotherapist [name] who will monitor participants and their safety while performing the strength tests

5. Afterwards participants will be given a printout of the TQR questionnaire and the Hooper Index to complete for the next day. Participants will be given their course of supplementation, either placebo or KSM-66, and instructed to take one a day for 28 days
6. The following day, baseline measures for the muscle recovery will be collected remotely at midday via Whatsapp or Zoom, and at the same time participants will start supplementation of either KSM-66 or placebo
7. Fourteen days later, participants perform the muscle strength tests in the evening at the club gym. Similar to before, the team will consist of the author ([name]), [name], who will assist with data collection and physiotherapist [name] who will monitor participants' safety while performing the strength tests

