8. Afterwards participants continue with the regular gym training session. Printouts of TQR and Hooper Index questionnaires are given to participants for the next day
9. The following day muscle recovery measures are collected remotely via Whatsapp or Zoom at midday
10. An additional fourteen days later, participants finish supplementation and perform the muscle strength tests in the gym with identical circumstances (staff, equipment, temperature) as the previous two gym sessions
11. The following day muscle recovery measures are collected remotely via Whatsapp or Zoom at midday. The trial finishes
12. The analysis of data begins
13. The process dissemination of results and findings begins

The study is designed with ease of participation in mind, but there will be inconveniences for participants who forget to take the intervention or fill out the food diary. To alleviate this, participants will be notified (with permission via the consent form) over Whatsapp with reminders during the 28 days supplementation. Additionally, there will be a check-in session a week after supplementation starts, to assess participant satisfaction and compliance.

Resources

Primary resources will consist of raw data through observation obtained from gym equipment and hand grip dynamometer and first-hand accounts from participants when answering

subjective questionnaires and food diaries. Secondary resources will consist of Excel and Google sheets to store the data, SPSS software to analyse the data, and Nutritics software to analyse the dietary intake.

The facility where the baseline and post-supplementation muscle strength tests are performed will take place at the club gym for CE Seagull (located at [name]). Participants will be familiar with the facility and its equipment due to previous weekly gym training sessions prior to any measurements.

Applicability and limitations

Applicability

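### The withdrawal rule has only two grounds, and no visible step re-checks the health exclusions or lets the researcher stop the capsules if a player newly meets one or has a suspected reaction

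*Combined protocol and SAP*

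**What the plan says.** **Entry.** Methodology, Selection criteria, excludes players with the health conditions at issue. Two entries carry a reason tied to the product: "Thyroid conditions (due to interaction with cortisol") and "Allergies to nightshades such as tomato, aubergine, potatoes and peppers (as ASH is an herb in the nightshade group"). The others (diabetes or certain autoimmune conditions, pregnancy, medication or contraceptives) are justified only by not disturbing treatment, for example "Medication or contraceptives (to not interfere with existing treatment").

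**Exit.** The rule that follows the list is: "The withdrawal criteria will be participants who request to withdraw and do not wish to proceed, or do not complete the required study tests."

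**Health information and contacts.**
- Work plan, step 1, alongside consent: "Information about age, BMI, years of practice and health history is collected."
- Work plan, step 5, at the baseline visit: "Participants will be given their course of supplementation, either placebo or KSM-66, and instructed to take one a day for 28 days."
- End of the Work plan: "there will be a check-in session a week after supplementation starts, to assess participant satisfaction and compliance." WhatsApp reminders also run through the 28 days.
- Work plan, step 4, on the physiotherapist: "who will monitor participants and their safety while performing the strength tests." Step 7 says much the same for the day-14 visit.

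**Risk statements.** Benefit / risk ratio foresees an undiagnosed illness or nightshade allergy leading to side effects. It calls this unlikely because athletes usually have medical staff who check their health. Ethical considerations gives players information on side effects and a right to leave at any time.

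**The concern.** An exclusion that bars the first capsule for a reason tied to the product argues equally against the next one. A player may be found to have a thyroid condition, or react as if allergic, in the second week. She then meets a criterion that would have kept her out. Yet neither withdrawal ground covers her unless she asks to leave or misses the tests.

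The stake is safety, mainly for the two exclusions with a product-related reason. For pregnancy, diabetes, autoimmune conditions and medication, the plan's own reasoning supports a narrower point: conduct during dosing should be consistent with the entry rule. Staff are blinded, so any stopping rule has to work without knowing which capsule the player takes.

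**Working it through.** The plan has no figure on this point to reproduce. The check has two parts.

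**1. Does any visible step fill the gap?**
- Health history (step 1): collected once. Equitable selection of subjects puts the presentation a month before the study so that players have time to consent, so the information could be weeks old at the first capsule.
- Capsule hand-out (step 5): the course is given at baseline, with no eligibility question beforehand.
- Week-1 check-in: its stated purpose is satisfaction and compliance.
- Reminders and researcher contact: a channel to the player, but with no health question or action attached.
- Physiotherapist: safety cover during the strength tests only.
- Right to leave: depends on the player acting.
- Club medical staff: offered as a reason why risk is low, not as a trial procedure.
- Club liaison who knows the players' health: helps with recruitment and selection.

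Count: two withdrawal grounds, no visible re-check of exclusions during dosing, and no visible stopping rule for the researcher.

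**2. How large could it be?**

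Inputs from the plan: 30 players, 15 per group (Sample size); 28 daily capsules. Assumption: a proportion p of 1% to 5% newly meet any exclusion during dosing, players independent.

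Expected cases are n × p, and the chance of at least one is 1 − (1 − p)^n.

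| p | Cases in 30 | P(at least one in 30) | Cases in 15 on active | P(at least one in 15) |
|---|---|---|---|---|
| 1% | 0.3 | 1 − 0.99^30 = 26% | 0.15 | 1 − 0.99^15 = 14% |
| 5% | 1.5 | 1 − 0.95^30 = 79% | 0.75 | 1 − 0.95^15 = 54% |

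Further capsules after onset. Take the first capsule as day 1, with onset just after the capsule on day k and k equally likely from 1 to 28.
- Nothing stops the capsules: mean of (28 − k) = 378/28 = 13.5, range 0 to 27.
- Check and stop at day 8 (week-1 check-in) and day 15 (mid-trial visit, 14 days after the first capsule), each after that day's capsule. The sums are 28 for k = 1 to 8, 21 for k = 9 to 15, and 78 for k = 16 to 28. The mean is 127/28 = 4.5, range 0 to 12.
- Mid-trial visit counted from the baseline visit instead, so day 14: (28 + 15 + 91)/28 = 134/28 = 4.8, range 0 to 13.

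Half the cases would be on placebo. The expected active capsules per case are therefore 13.5/2 = 6.75 without a rule and 4.54/2 = 2.3 with one.

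**The case against.** Several objections have force.

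- **The consent form is not visible.** The summary says it covers supplement safety and the right to drop out. A duty to report a pregnancy, a new medicine or a reaction could well be there. This stands, and it limits the finding to the visible text. A duty on the player would still not give the researcher a ground to stop capsules under Selection criteria.
- **The plan is silent; it does not order dosing to continue.** A reader might infer that a player with a new exclusion must stay on capsules. The text does not say so, and she can leave at any time. What stands is that the researcher has no stated ground to act if she does not.
- **The rate is assumed and pooled.** It probably reflects new medication or contraceptives more than thyroid disease or allergy. A reader might take the 26% to 79% as a chance of product-related harm. The documents do not support that: they give no rate for any exclusion, and only about half the players take active product.
- **The capsule saving is optimistic.** The 13.5 assumes that no player stops by herself. The 4.5 assumes that every case is recognised and disclosed, although players may decline questions. The difference is an upper bound.
- **Repeated questions cannot find a condition the player does not know about.** This is correct. For the undiagnosed illness or allergy foreseen in Benefit / risk ratio, only a suspected-reaction clause helps.

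One counterweight: Benefit / risk ratio says no adverse effects have been reported. Potential side effects, however, cites a 60-day trial of 600 mg KSM-66 with 6 adverse events on ashwagandha and 5 on placebo. Causation is unclear, but complaints during dosing are plausible, and no handling is stated for them.

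**Conclusion.** The gap holds on the visible text, and the change is worth making. The safety argument is strongest for thyroid conditions and nightshade allergy, where the plan's own reasons concern the product. For the other exclusions the argument is consistency with the entry rule.

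The size is illustrative only. It rests on an assumed 1% to 5% pooled rate, independence between players and uniform onset. On those terms fewer than one case on active product is expected.

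A reader might infer that the omission biases the results or undermines the trial's conclusions. Nothing in the documents shows that. It is a safety and conduct gap of low expected frequency, and no estimate of the trial is shown to change.

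**What to change.** 1. **Ask again.** Repeat the exclusion questions at the baseline visit before capsules are handed out, at the week-1 check-in and at the day-14 visit. Use a short self-completed card returned to the main researcher only, and keep the right to decline. Give every player the written list, so that one who declines can still stop the capsules herself.
2. **Add a stopping rule to Selection criteria.** The researcher stops capsules, in either arm and without unblinding, for pregnancy; for a newly diagnosed thyroid, diabetic or autoimmune condition; or for a suspected nightshade or product reaction. Any new regular medication or contraceptive is reported, and capsules are stopped in line with the entry exclusion.
3. **Separate stopping capsules from leaving the study.** Questionnaires continue. Strength tests continue only if the player is medically fit. Her data are analysed as randomised. This also limits the loss of data with 15 players per group.

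Cost: a few sentences of protocol text and 30 × 3 = 90 short cards of a few minutes each, with no new visit. The questions are sensitive, and Integrity says all collaborators are employed by the club, so the answers must be kept from club staff. A player or two may be found ineligible or taken off capsules.
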